2.2 STUDY ENDPOINTS

Primary Endpoint

Metastasis-Free Survival (MFS)

Secondary Endpoints

- Overall Survival (OS)
- Time to symptomatic progression
- Time to initiation of cytotoxic chemotherapy
- Progression-Free Survival (PFS)
- Time to Metastasis (TTM)

Other Evaluations

- Health-related quality of life and prostate cancer-specific symptoms
- Type, incidence, toxicity, timing, seriousness, and relatedness of adverse events and laboratory abnormalities
- PSA response
- Time to PSA progression
- Population pharmacokinetics
- Exploratory biomarkers

ARN-509-003 Statistical Analysis Plan v7.0 26 June 2017

Page 6 of 34

- Assessment of ventricular repolarization [Appendix 8 of the protocol]
- Second progression-free survival (PFS2)

3. RANDOMIZATION

Upon verification of inclusion and exclusion criteria, eligible patients will be centrally randomized in a 2:1 ratio to either ARN-509 or placebo. The randomization will be stratified as follows:

- PSADT (≤ 6 months vs. > 6 months)
- Bone-sparing agent use: Yes vs. No
- Loco-regional disease: N0 vs. N1

In order to ensure accurate and consistent determination of PSADT, the Interactive Voice Recognition System (IVRS) will also provide PSADT calculations (using a linear regression model of the natural logarithm of PSA and time) based on PSA values entered by the sites prior to randomization.

4. SAMPLE SIZE DETERMINATION

The primary efficacy analysis will be event-driven and will take place when approximately 372 MFS events have occurred. The study provides 90% power to detect a 30% reduction in the risk of developing metastases (HR = 0.70) for patients receiving ARN-509, with a 2-sided α of 0.05.² Based on an assumed median MFS of 25 months in the placebo group, this treatment effect represents an increase in the median MFS of approximately 11 months (from 25 months to 36 months). Assuming an accrual period of 24 months (with 75% of the patients accrued in the second year), approximately 1200 patients will need to be randomized.

The study was also designed to provide 85% power to detect a 25% reduction (HR = 0.75) in the risk of death for patients receiving ARN-509, based on an assumed median OS of 49 months in the placebo group. This treatment effect represents an increase in the median OS of approximately 16 months (from 49 to 65 months).

5. INTERIM ANALYSIS

There will be no interim analysis for the primary endpoint (MFS) and for the secondary endpoints of TTM and PFS. There will be 1 interim analysis for time to symptomatic progression, and up to 2 interim analyses for OS and time to initiation of cytotoxic chemotherapy; see Section 7.5.3 for details.

6. INDEPENDENT DATA MONITORING COMMITTEE

An independent third-party Data Monitoring Committee (IDMC) will be established to ensure the overall integrity and conduct of the study.

The IDMC will review the progress of the study and cumulative unblinded safety data on a periodic basis (e.g., a minimum of two review meetings per year) as well as review the efficacy analysis when necessary. In addition to the review meetings, blinded (or unblinded,

ARN-509-003 Statistical Analysis Plan v7.0 26 June 2017

Page 7 of 34

if necessary) listings of serious adverse events will be provided to the IDMC on a monthly basis.

Following each review meeting, the IDMC will recommend to the Sponsor whether to continue the trial unchanged, modify the conduct of the study, or terminate the study early. Rules for early termination, modification or continuation of the study, as well as how these recommendations will be made to the Sponsor and Health Authorities will be outlined in a separate IDMC Charter.

The IDMC will be composed of 3 external members [2 physicians and 1 biostatistician] not associated with the conduct of the study. The Sponsor will also designate an independent biostatistician not affiliated with the project to prepare and provide study data to the IDMC. Complete details regarding the composition and governance of the IDMC will be outlined in the IDMC Charter.

Periodic adverse event data review will also be performed by designated members of the Sponsor's primary study team and will be blinded to treatment assignment with adverse event data from both treatment groups combined. Any safety issues of concern identified by the primary study team that require notification of the IDMC will be communicated as described in the IDMC Charter.

7. STATISTICAL METHODS

The primary objective of the study is to evaluate the efficacy of ARN-509 compared to placebo in patients with high risk NM-CRPC as measured by metastasis-free survival (MFS), based on blinded independent central review (BICR) of tumor assessments.

7.1 ANALYSIS POPULATIONS

Full Analysis (Intent-to-Treat) Population [ITT]: All eligible patients who are randomized into the study, with study drug assignments designated according to initial randomization, regardless of whether patients receive study drug or receive a different drug from that to which they were randomized to will be included in the analyses of all efficacy and clinical benefit endpoints and patient characteristics.

Safety Analysis Population [SAFETY]: All patients who receive at least one dose of study drug, with treatment assignments designated according to actual study treatment received will be the primary population for evaluating safety and treatment compliance and administration.

- **Population Pharmacokinetics Population [PK]**: Subset of the safety analysis population that was randomized to the ARN-509 treatment group and that has at least one PK sample collected.
- **Biomarker Population**: Subset of the safety analysis population that has at least 1 biomarker sample collected.

7.2 **DEFINITIONS**

Study Day: Study day will be calculated in reference to the date of randomization for randomized untreated subjects and in reference to the date of first dose for treated subjects.

ARN-509-003 Statistical Analysis Plan v7.0 26 June 2017

Page 8 of 34

Study Day 1 corresponds to the date the subject was randomized into the study or to the date of first dose the subject was treated.

Baseline Value: Unless otherwise specified, the baseline value will be defined as the closest measurement prior to the first dose of study drug. Change from baseline will be defined as (post-baseline value – baseline value).

Treatment Duration: Treatment duration will be defined as the duration of time from the date of the first dose of study drug to the date of last dose of study drug + 1 day.

Time to event: Time to event calculations will be defined as the time from randomization to date of event + 1 day. Time to event or duration of event endpoints will be based on the actual date of the event, not visit number or visit label.

Survival Follow-Up Phase: The survival follow-up phase will start from the safety followup visit (28 days following the last dose of study drug) and continue through the end of the study.

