### 13.1 ANALYSIS POPULATIONS

**Full Analysis (Intent-to-Treat) Population [ITT]:** All eligible patients who are randomized into the study, with study drug assignments designated according to initial randomization, regardless of whether patients receive study drug or receive a different drug from that to which they were randomized to will be included in the analyses of all efficacy and clinical benefit endpoints and patient characteristics.

**Safety Analysis Population [SAFETY]:** All patients who receive at least one dose of study drug, with treatment assignments designated according to actual study treatment received will be the primary population for evaluating safety and treatment compliance and administration.

- **Patient Report Outcomes Population [PRO]:** Subset of the safety analysis population that has completed at least the baseline assessment (Cycle 1 Day 1) of either FACT-P or EQ-5D questionnaires.
- **Population Pharmacokinetics Populations [PK]:** Subset of the safety analysis population that was randomized to the apalutamide treatment arm and that has at least one PK sample collected.
- **Biomarker Population:** Subset of the safety analysis populations that has at least 1 biomarker sample collected.

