7.3 ANALYSIS OF STUDY CONDUCT

All patients randomized into the study will be summarized by treatment group as randomized. The randomization stratification factors will be listed and tabulated as recorded in the IVRS by treatment group as randomized.

The number of patients who are in the ITT and SAFETY populations will be summarized by treatment group and overall.

Study treatment administration, duration of follow-up, discontinuation from study treatment and the reasons for discontinuation will be summarized by treatment group for all randomized patients. In addition, major protocol deviations and eligibility violations will also be summarized by treatment group. Protocol violations for this study include, but are not limited to, the following:

- Failure to meet inclusion/exclusion criteria
- Use of a prohibited concomitant medication
- Dose modifications that are not within the protocol specifications
- Any other deviation that presents significant risk or safety concerns to the patient

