7.5 EFFICACY ANALYSES

The following section outlines the planned analyses of the primary and secondary efficacy outcomes of the study.

Efficacy analyses will be performed on the ITT population, incorporating the randomization stratification factors as documented on the IVRS, unless otherwise specified.

Time-to-event endpoints will be summarized using the Kaplan-Meier method ³ and displayed graphically where appropriate. Median event times and 2-sided 95% confidence interval for each median will be provided. Cox proportional-hazard models, including the stratification factors at baseline, will be used to estimate the hazard ratio (HR) and its 95% confidence interval (CI).

Response endpoints (eg, PSA response rate) will be summarized using descriptive statistics for categorical data by treatment group. The relative risk (treatment:control) will be reported along with the associated 2-tailed 95% CIs. The two treatment groups will be compared using the stratified Mantel-Haenszel test; Fisher's exact test may be used if the expected counts in some cells are small.

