7.5.2 Primary Endpoint (MFS)

The primary efficacy endpoint is metastasis-free survival (MFS), defined as the time from randomization to first evidence of BICR-confirmed radiographically detectable bone or soft tissue distant metastasis (simply referred to as "metastasis" from this point forward) or death due to any cause (whichever occurs earlier) + 1 day.

ARN-509-	-003					
Statistical	Analysis	Plan	v7.0	26.	June	2017

Page 11 of 34

MFS data for patients without metastasis or death will be censored on the date of the last tumor assessment (or, if no tumor assessment was performed after the baseline visit, at the date of randomization + 1 day).

Additional censoring rules will vary according to whether the analysis is performed for US or ex-US regulatory purposes, as follows; both results will be provided in the clinical study report.

Scenario	US regulatory guidance	ex-US regulatory guidance ⁴
Data from patients who are lost to follow-up or whose disease progression (development of metastasis) or death occurs after 2 or more consecutively missing or unevaluable tumor assessments	Censored on the date of the last tumor assessment that the patient was known to be metastasis-free	Time of progression will be determined using the first date when there is documented evidence of progression or death (whichever occurs earlier) regardless of missed or unevaluable tumor assessments
Patients that receive new systemic anti-cancer therapy prior to documented disease progression (development of metastasis) or death	Censored on the date of the last tumor assessment prior to the start of the new systemic anti-cancer therapy	Time of progression will be determined using the first date when there is documented evidence of progression or death (whichever occurs earlier) regardless of change of therapy

Disease progression (development of metastasis) will be assessed by an independent core imaging laboratory using the Response Evaluation Criteria in Solid Tumors (RECIST v1.1).⁵ The appearance of new (or distant) metastatic lesions denotes disease progression. For new bone lesions detected on bone scans, a second imaging modality (e.g., CT or MRI) will be required to confirm progression.

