7.5.3.1 Overall Survival

OS will be defined as the time from randomization to the date of death due to any cause + 1 day. Patients who are alive at the time of the analysis will be censored on the last known date that they were alive. In addition, the following censoring rules will apply:

Scenario	Date of Censoring
Patients with no post-baseline information	Censored on the date of randomization + 1 day
Patients who are lost to follow-up or who withdraw consent for further follow-up	Censored on the last known date that they were alive

Survival rate at 1-, 2-, 3- and 5-year will be estimated using the Kaplan-Meier method. Additional sensitivity analyses are provided in Section 7.8.

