7.9.5 Efficacy (MFS and PSA Response) Analyses by Formulation

The primary MFS analysis and statistical inference will be based on the ITT population regardless of the formulation as defined in section 7.5.2. In order to assess the consistency of treatment benefit (relative to ITT analysis), a supplemental analysis by formulation subgroup will be performed on the BICR derived MFS endpoint and PSA response.

The following formulation subgroups will be used in the analysis:

- 1. Capsule only, tablet only and capsule + tablet
- 2. Two groups based on greater duration of exposure on specific formulation: greater duration on capsule versus greater duration on tablet.

The MFS subgroup analysis will include the following:

- Number of events and censored
- Distribution of MFS endpoint using the Kaplan-Meier method
- Non-stratified estimate of the hazard ratio and its associated 95% confidence interval using the Cox model.

ARN-509-003		
Statistical Analy	sis Plan v7.	0 26 June 2017

Page 23 of 34

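### Does the word *eligible* in the ITT definition allow randomised patients later found ineligible to be dropped from the primary MFS analysis?

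*SAP*

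**What the plan says.** SAP 7.1 defines the Full Analysis (Intent-to-Treat) population as "All eligible patients who are randomized into the study, with study drug assignments designated according to initial randomization", and adds that this holds "regardless of whether patients receive study drug or receive a different drug from that to which they were randomized to". Protocol 13.1 opens in the same way, "All eligible patients who are randomized into the study", and so does section 2.5.1 of the patient-reported outcomes SAP.

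The set carries the main results. SAP 7.5 states that "Efficacy analyses will be performed on the ITT population", and SAP 7.9.5 that "The primary MFS analysis and statistical inference will be based on the ITT population".

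SAP 7.3 foresees some randomised patients who did not meet the entry criteria: "major protocol deviations and eligibility violations will also be summarized by treatment group". The same section reports how many patients are in the ITT and safety sets, by treatment group and overall.

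On the order of events, Protocol 5.1 and 8.2 and SAP section 3 all put the eligibility check before randomisation. Under Protocol 8.2 the medical monitor confirms eligibility first. Protocol section 4 allows no waivers.

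**The concern.** An intent-to-treat set normally means all randomised patients, with no qualifier. Here a qualifier appears in all three definitions, and the clause that widens the set speaks only of the drug received, not of eligibility. The safety set, defined next in SAP 7.1, has no such qualifier. On a strict reading, a dosed patient later found ineligible would count for safety but not for efficacy.

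The plan expects such patients, since it tabulates eligibility violations. It also gives explicit rules for other awkward cases: MFS is censored, "if no tumor assessment was performed after the baseline visit, at the date of randomization + 1 day", and OS has a rule for "Patients with no post-baseline information". There is no matching sentence for patients found ineligible after randomisation, and SAP 7.8 lists no sensitivity analysis on all randomised patients.

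The stake would be the integrity of the primary comparison. If membership of the set could be decided after outcomes were known, the protection that randomisation gives would be weakened. That matters most here because absence of distant metastasis is an entry criterion, its appearance is the main component of the endpoint, and the same central imaging review assesses both.

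**Working it through.** **1. The plan's own figure.** Inputs from SAP section 4: hazard ratio 0.70, two-sided alpha 0.05, power 90%. Allocation 2:1 is from SAP section 3.

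Events = (1.960 + 1.282)² / [(2/3)(1/3)(ln 0.70)²] = 371.7, which rounds up to the stated 372.

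Power at 372 events = Φ(|ln 0.70| × √(372 × 2/9) − 1.960) = 0.900.

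The design figure reproduces, and the word *eligible* does not enter it.

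**2. What would happen if patients were dropped.** The documents give no ineligibility rate, so the shares below are assumptions. Suppose the 372 events are counted in all randomised patients and a share is then removed, with events lost in proportion:

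| Share dropped (assumed) | Events left | Power |
|---|---|---|
| 0% | 372 | 90.0% |
| 1% | 368.3 | 89.7% |
| 3% | 360.8 | 89.1% |
| 5% | 353.4 | 88.5% |
| 10% | 334.8 | 86.8% |

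If the 372 events are counted within the analysed set, power stays at 90.0%.

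**3. Effect on the hazard ratio.** Take exponential MFS with medians of 25 months and 25/0.70 = 35.7 months. If patients are removed without regard to outcome, events and person-time shrink by the same factor, so each arm's hazard is unchanged. Removing 32 of 800 apalutamide patients multiplies both by 0.96; removing 12 of 400 placebo patients multiplies both by 0.97. Either way the expected hazard ratio stays at 25/35.7 = 0.700. This does not cover removal that depends on outcome, so the question is whether the plan provides for any removal at all.

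**4. How the documents use the word.**

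- *Before randomisation.* Protocol 3.1, 5.1 and 8.2 and SAP section 3 use eligibility for a status checked and confirmed before randomisation. In that sense, eligible patients who are randomised are simply those who passed the check and were randomised.
- *After randomisation.* Neither document describes a later adjudication of eligibility, a list of grounds for removal from the ITT set, or a per-protocol set.
- *Violations.* SAP 7.3 opens with all randomised patients, as randomised, and within that frame tabulates eligibility violations by treatment group. It treats them as deviations to report.
- *Stopping treatment.* Protocol section 10 lists a protocol violation among the reasons for stopping study drug, and says that stopping does not by itself take the patient out of the study. Such patients go into long-term follow-up.

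**The case for a change.** The strongest case for acting is that a check before randomisation does not answer a question about errors found after it, and SAP 7.3 shows that the plan expects some. Protocol section 11 also lets the sponsor decide case by case whether a violation leads to withdrawal. If the word is redundant, removing it costs nothing; if it is not, it opens the primary set to exclusions.

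Part of this stands. No sentence states outright that such patients remain in the ITT set, and a definition without the qualifier would be cleaner.

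The rest is weaker. Section 11 concerns a patient's withdrawal and does not mention his data or the analysis set; the OS rules in SAP 7.5.3.1 keep patients who withdraw consent for follow-up, as censored. The contrast with the rules for missing post-baseline data does not carry far either. Those are censoring rules, needed because such patients have nothing from which to date an event or a censoring time. A patient found ineligible but followed normally has scans and survival data, so the ordinary rules already apply. The overlap between entry criterion and endpoint would matter if late re-reading of baseline scans led to removal, but neither document sets up such a step. Finally, the ITT count is reported by treatment group, so a gap between randomised and ITT numbers would show, and SAP section 1 requires departures from the plan to be described in the study report.

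**Conclusion.** The concern does not call for a change. The qualifier is a redundant word that analysts would read sensibly: the ITT set is everyone randomised, analysed as randomised. That reading rests on the documents' consistent use of eligibility as a status confirmed before randomisation, on the full-analysis and intent-to-treat label, and on the absence of any planned exclusion. To read the word as a licence to exclude, one has to assume a retrospective judgement of eligibility that neither document contains.

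No planned result moves: 372 events, 90.0% power and about 1,200 patients all stand. The losses of 0.3 to 1.5 percentage points of power at 1% to 5% dropped (90.0 − 89.7 and 90.0 − 88.5) depend on assumed exclusions that the plan does not make, and they vanish if events are counted in the analysed set. Dropping the word would be an editorial tidy-up with no effect on the analysis.

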### **3.1.1 Crossover Option in the Event of Unblinding**

At the time of study unblinding and in the event of a positive study result, all subjects currently receiving placebo will have the opportunity to receive active therapy with apalutamide (refer to Appendix 10).

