**APPENDIX 10: CROSSOVER TO OPEN LABEL APALUTAMIDE AFTER STUDY UNBLINDING**

At the time the decision is made to unblind the study, investigators will be notified by the sponsor. Subjects randomized to placebo who are currently on study treatment will be offered treatment with open-label apalutamide at 240 mg/day.

Subjects previously randomized to apalutamide will continue on protocol and follow the current schedule of activities (Appendix 1, with modifications below) and will be given open-label apalutamide.

For subjects who crossover from placebo to apalutamide, radiographic scans will no longer be required for the study and submitted for blinded central independent review. Subjects will be followed for progression per Investigator decision including symptoms, radiographic scans or PSA. PSA data submitted to the central laboratory will no longer be blinded. In addition, for all subjects, PK samples will no longer need to be collected at the time of unblinding.

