**Table 3 Time and Events Schedule for Subjects on Placebo Crossing Over to Open Label Apalutamide**

Activities and Forms to be Completed	Screening	Crossover Phase			Posttreatment		
	Visit from last treatment cycle on main study can be used	Cycle 1 Day 1	D1 C1-C6, D1 of every 2 cycles starting at C7 to C13, then D1 of every 4 cycles unless otherwise specified	Every 16 weeks	End-of-Treatment [1]	Safety Follow-up [2]	Long-term Follow-up [3]
Informed Consent	X						
Eligibility Criteria	X						
Study Drug Administration							
Apalutamide [4]		X→	→				
Study Drug Compliance [5]			X		X		
Laboratory Studies							
Hematology [6]	X	X[6]	X		X		
Blood Chemistry [6]	X	X[6]	X		X		
PSA [7]	X	X[6]	X		X		
Testosterone [7]	X	X[7]		X	X		
Thyroid-Stimulating Hormone [7]	X	X[7]		X	X		
Fasting Lipid Panel [7]	X	X[7]		X	X		
Efficacy							
ECOG	X	X	X		X		
Medical Resource Utilization		X	X				X
Progression on first subsequent therapy [8]	X			X			X
Survival [3]							X
Patient Reported Outcomes							
FACT-P and EQ-5D[11]		X		X	X		X
Safety							
Physical Examination [9]	X	X	X		X		
Vital Signs [10]	X	X	X		X		
Adverse Events	Continuous until 28 days after the last dose of apalutamide						
Concomitant Medications	Continuous until 28 days after the last dose of apalutamide						

CT=computed tomography; ECOG=Eastern Cooperative Oncology Group; PSA=prostate specific antigen

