9.	Physical Examination: At Screening, a complete physical examination of major body systems. During subsequent visits, either a full or abbreviated physical exam will be performed. New abnormal physical exam findings must be documented and followed by a physician or other qualified staff at the next scheduled visit. Body weight will be recorded at Screening and at every scheduled visit during treatment and at the end of treatment.
10.	Vital Signs: Body temperature, blood pressure, pulse and respiratory rate will be performed after resting for 5 minutes at every scheduled visit during treatment and at the end of treatment.
11.	FACT-P and EQ-5D questionnaires: Patients will complete the FACT-P and EQ-5D at the clinic PRIOR to any other clinical activity on Cycle 1 Day 1, then Day 1 of every Cycle up to Cycle 13, then Day 1 of every other cycle, and at the End-of-Treatment Visit. During survival follow-up contact every 4 months via clinic visit or telephone up to 12 months post-progression

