7.4.3 Study Drug Administration

The SAFETY population will be used to summarize drug exposure, treatment compliance, and dose modifications by treatment group as treated.

Treatment duration will be defined as the duration of time from the date of the first dose of study drug to the date of last dose of study drug + 1 day.

The total cumulative dose in milligrams (mg) will be calculated as 30 or 60 mg multiplied by the number of capsules or tablets taken. The number of capsules or tablets taken will be calculated based on the number of capsules or tablets dispensed at the study visits minus the number of capsules or tablets indicated as having been returned.

The overall treatment compliance will be defined as the total dose in mg taken during the study divided by the expected total dose in mg. A subject's expected total dose will be calculated as the assigned dose per day multiplied by treatment duration. Each patient should be taking 8 capsules or 4 tablets per day maximum while on the study. For patients with dose reductions, the expected number of capsules or tablets will be reflective of the new dose with a reduced number of total capsules or tablets.

Dose reduction or interruption and the reason for the dose reduction or interruption will be summarized by treatment group as treated.

ARN-509-003 Statistical Analysis Plan v7.0 26 June 2017

Page 10 of 34

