2.5.4 Time to Degradation for FACT-P

Degradation/deterioration is defined based on a clinically meaningful threshold for each specific PRO scale. Table 2 summarizes the threshold values for determining a FACT-P degradation/deterioration. Time to degradation/deterioration will be defined as the time interval from randomization to the first date a patient experiences a clinically meaningful threshold change. Subjects who did not experience degradation/deterioration will be censored at their last available assessment. Assessments in both treatment and follow-up phases will be included to determine the time of event or censoring. For subjects receiving subsequent anticcancer therapy, only the assessments on or before the subsequent therapy will be included in analysis. Time to degradation/deterioration will be compared between 2 treatment groups.

Change thresholds for deterioration on the FACT-P PCS, TOI, and FACT-P Total scales are based upon an article,⁵ which provided clinically meaningful change estimates in a prostate cancer sample based upon an anchoring methodology. The FACT-G scales (PWB, SFWB, EWB, FWB, and the FACT-G) were not addressed in that article, and so the clinically meaningful change estimates for those scales are derived from an earlier article,⁶ which

ARN-509-003	
PRO Statistical Analysis Plan v2.0 26 June 2017	Page 7 of 17

reports normative values from a large sample from the general population for the FACT-G scales. Taking one half the standard deviation is equivalent to finding a 0.5 effect size. Using this distributional technique, the clinically meaningful change estimates are defined in Table 3 below.

Scale/Sub-Scale	Threshold for definition of progression/deterioration
Physical Well-Being (PWB)	3
Social/Family Well-Being (SFWB)	3
Emotional Well-Being (EWB)	3
Functional Well-Being (FWB)	3
FACT-G (General) Scale	9
Prostate Cancer Subscale (PCS)	3
Trial Outcome Index (TOI)	9
FACT-P Total Scale	10
FACT-P Pain Scale	2
FAPSI-8	3

 Table 2:
 Time to Deterioration Thresholds for FACT-P Scales

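### Neither SAP ends the placebo period at crossover, so safety, exposure and PRO reports that include post-crossover data are undefined or mix placebo with apalutamide time

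*SAP*

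**What the plan says.** **Crossover.** Protocol 3.1.1 provides for a switch to apalutamide: "At the time of study unblinding and in the event of a positive study result, all subjects currently receiving placebo will have the opportunity". Appendix 10 gives the eligibility criteria and a separate schedule, headed as a crossover phase with cycles restarting at Cycle 1. AE collection in that schedule (Table 3) is "Continuous until 28 days after the last dose of apalutamide". FACT-P and EQ-5D also continue. Footnotes 1, 2 and 5 of Table 3 call the open-label product study drug.

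**Safety and exposure.** SAP 7.1 builds the safety population from "All patients who receive at least one dose of study drug, with treatment assignments designated according to actual study treatment received". SAP 7.4.3 defines treatment duration as the "duration of time from the date of the first dose of study drug to the date of last dose of study drug", plus one day. SAP 7.6.1 and the table shell in SAP Appendix 2 carry treatment-emergent AEs to 28 days after the last dose of study drug. SAP 7.2 takes baseline as the closest value before the first dose of study drug. None of these mentions crossover.

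**PRO.** SAP 7.7.3 and PRO SAP 2.5.1 use the ITT population as randomized. PRO SAP 2.5 puts every assessment into the time-to-event analysis, and 2.5.4 says: "Assessments in both treatment and follow-up phases will be included to determine the time of event or censoring". The only cut is at subsequent anti-cancer therapy, which 2.5 describes as following discontinuation of study drug.

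**FACT-P schedule after crossover.** The Table 3 grid marks Cycle 1 Day 1 and every 16 weeks. Footnote 11 to the same table says Cycle 1 Day 1, "then Day 1 of every Cycle up to Cycle 13, then Day 1 of every other cycle".

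**Timing.** SAP 7.7.2 ties the PSA analysis to the primary MFS analysis. No cutoff is stated for the AE, exposure or PRO analyses.

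**The concern.** Both SAPs were finalised about three months after Amendment 8, yet their windows are written as if each patient took one treatment throughout. Once crossover starts, a placebo patient has a blinded placebo period followed by an open-label apalutamide period, and no rule separates them.

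Two stated objectives are at stake: evaluating the safety of apalutamide, and comparing PROs with placebo. If crossover time is counted under placebo, events on apalutamide enter the placebo column and real excesses shrink. If crossover patients are moved to the apalutamide column, their placebo time goes with them, and the placebo column keeps only patients who had stopped treatment or did not cross over, which is a selected group. For PROs, a first clinically meaningful drop on apalutamide would count as a placebo event. Reports after the primary analysis are part of the plan: SAP 7.5.3 and Appendix 1 provide for later analyses of symptomatic progression, OS and cytotoxic chemotherapy, and Protocol 15.6 projects about 65 months in total.

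**Working it through.** **1. When crossover can begin.** The earliest planned trigger is the primary analysis at about 372 MFS events. The plan's own figure reproduces. With HR 0.70, two-sided alpha 0.05, 90% power and 2:1 allocation (SAP 4; Protocol synopsis), the Schoenfeld formula gives

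events = (1.960 + 1.282)² / [(1/3)(2/3)(ln 0.70)²] = 10.51 / 0.02827 ≈ 372.

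With exponential MFS (medians 25 and 36 months), 400 and 800 patients, and accrual over 24 months with 75% in the second year, expected events are 366 at month 32 and 384 at month 33. This agrees with 24 + 9 = 33 months in Protocol 15.6.

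**2. At a cutoff before unblinding.** No placebo patient has received open-label drug, so the apalutamide share of placebo-arm time is 0%.

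**3. At later cuts, if crossover time is counted under placebo.** The following are assumptions, not document figures: crossover at month 33, uptake of 50% or 100%, other discontinuation of 0%, 10% or 20% a year (monthly hazard d), and a cut at month 45 or 65. Month 65 is the protocol's projected duration; month 45 is simply 12 months after crossover. Let λ0 = ln 2/25 and λ1 = ln 2/36.

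- Placebo patients on treatment at month 33: 400 × average over entry times e of exp[−(λ0 + d)(33 − e)].
- Placebo person-months before crossover (pre): 400 × average of {1 − exp[−(λ0 + d)(33 − e)]}/(λ0 + d).
- Person-months after crossover (post): uptake × number on treatment × {1 − exp[−(λ1 + d)(cut − 33)]}/(λ1 + d).
- Share f = post/(pre + post).

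| Other discontinuation | On treatment | Pre | f: 50%, month 45 | f: 50%, month 65 | f: 100%, month 45 | f: 100%, month 65 |
|---|---|---|---|---|---|---|
| 0% a year | 246 | 5,542 | 19.2% | 34.7% | 32.3% | 51.5% |
| 10% a year | 213 | 5,136 | 17.4% | 30.4% | 29.7% | 46.6% |
| 20% a year | 181 | 4,735 | 15.5% | 26.1% | 26.9% | 41.4% |

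Lowest: 871/(4,735 + 871) = 15.5%. Highest: 5,885/(5,542 + 5,885) = 51.5%. The number crossing over ranges from about 90 to 246 of 400.

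**4. Effect on a rate ratio, on the same reading.** With constant AE rates, a true ratio R appears as R/[(1 − f) + R·f]. For R = 2.0 this is 1.73 at f = 15.5% and 1.32 at f = 51.5%. For R = 1.5 it is 1.39 and 1.19.

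**5. The FACT-P schedules.** Four 28-day cycles are 16 weeks, so the Table 3 grid matches the main-schedule interval after Cycle 13. Footnote 11 asks for an assessment every cycle up to Cycle 13 and every other cycle after that. Both cannot apply to the same patient.

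**The case against.** **The main comparison is not touched.** Crossover requires unblinding and a positive result. A reader might infer that the safety and PRO comparisons at the primary analysis are contaminated. With a cutoff before unblinding they are not. This stands and limits the point to later reports, or to a first report whose cutoff is not fixed beforehand.

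**The safety text does not put apalutamide time under placebo.** A reader might infer that it does. SAP 7.1 goes by treatment actually received and could be read as placebo, apalutamide or split by period. SAP 7.6.1 defines relatedness against blinded study drug, and Appendix 10 distinguishes that from open-label apalutamide. This stands too: the safety column is undefined, not wrong. But Table 3 also uses study drug for the open-label product, so the window's end is not settled either.

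**Crossover-phase PRO scores may lie outside the window.** Appendix 10 names a crossover phase, whereas the PRO SAP knows only treatment and post-treatment phases, and its mixed model covers the treatment phase alone. For the mixed model this leaves the position unclear. For time to degradation it does not hold, because PRO SAP 2.5 includes all assessments.

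**As-randomized analysis is the stated ITT rule.** A cut at crossover would change the question asked. That is true in principle, but the PRO SAP already departs from pure as-randomized follow-up by cutting at subsequent therapy, so a cut at crossover follows its own approach.

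**Sampling frequency.** A reader might infer that crossover patients will be assessed for FACT-P far more often than the comparator, bringing first drops forward. That depends on footnote 11 being followed; under the grid there is no excess.

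**Conclusion.** The gap is real but limited. No rule in either SAP ends the placebo period at the first open-label dose. At a primary-analysis cutoff before unblinding the effect is nil. In later reports, the safety and exposure column is undefined for a patient who took both treatments, and PRO time to degradation keeps apalutamide-period scores under placebo unless crossover is declared a subsequent therapy, which neither SAP does.

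The documents give no figure for the effect. The 16-51% share and the diluted rate ratios are illustrations. They rest on assumed uptake, discontinuation and cut dates, on exponential MFS, and on crossover time being counted under placebo. The 100% uptake end also ignores the consent, organ-function and prior-therapy criteria in Appendix 10. The conflict between the Table 3 grid and footnote 11 needs no assumption.

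**What to change.** - **SAP 7.2, 7.4.3 and 7.6.1:** for crossover patients, end the placebo exposure and treatment-emergent period on the day before the first open-label dose. Report later events and exposure in a separate placebo-to-apalutamide column with its own baseline.
- **PRO SAP 2.5 and 2.5.4:** use only assessments before the first open-label dose, and censor time to degradation at the last of these when no event has occurred. This mirrors the existing handling of subsequent therapy.
- **Protocol Appendix 10, Table 3:** reconcile the FACT-P grid with footnote 11.

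The cost is wording in two SAPs, one extra table column and a correction to Table 3, with no new data. The downside is slightly shorter placebo observation in later reports. The rules should be settled before any post-crossover data are analysed, so that the choice is not made after seeing them.
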